11.3 Documentation and reporting of adverse events by investigator

All AEs as well as any SAE that occur throughout the study must be documented in accordance with the instructions for the completion of (S)AE reports in clinical studies. If possible, AEs should be assigned to be either unrelated (corresponding to unrelated or unlikely related) or related (corresponding to probably, possibly or definitely related) to the IMP or the IMD, or both, as this will be important for evaluation of the safety of BF-200 ALA or the PDT lamp.

The following approach will be taken for documentation:

- **All AEs** during the study (whether serious or non-serious) must be documented.
- If the severity category of an AE changes, the date of change and the new severity category must be documented.
- If the AE is serious (see [Section 11.1.2](#)), the investigator must complete, in addition to the “Adverse Event” page in the eCRF, a “Serious Adverse Event/Expedited Report from a Clinical Trial for Combination products” (SAE report) form at the time the investigator became aware of the SAE. This form must be marked as “initial” and be sent immediately (within 24 h) to the sponsor’s Pharmacovigilance department by email or fax (according to Biofrontera’s Standard Operating Procedure (SOP)). SAEs must be identified as such in eCRF by stating the applicable SAE criteria that were met.
- When a “significant overdose” of IMP occurs without an AE or in other situations where the sponsor requires an expedited report without an AE (see [Section 11.1.3](#)), this information should be provided by the investigator via the “SAE report” form. It should be clearly stated that no AE was observed. In this case, there is no need to complete the “Adverse Event” page in the eCRF.
- The following details regarding AEs are required:
 - confirmed medical diagnosis or symptoms (if applicable)
 - location (treatment area(s))
 - category: general, application site skin reaction, application site discomfort or new lesion
 - time frame (by providing start/stop date and time)
 - severity and date of change of the respective severity category if applicable (see [Section 11.1.1](#)). On the first day of AE occurrence only the maximum severity has to be documented.
 - outcome (recovered/resolved, recovering/resolving; recovering with sequelae, not recovered/not resolved, fatal, unknown)
 - action taken (with reference to concomitant medications/treatments)
 - seriousness criteria (if applicable), and

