14 STATISTICAL PROCEDURES

14.1 General considerations

The principal features of the statistical analysis are described in this section. Technical details of the statistical analyses will be specified in a statistical analysis plan (SAP). The SAP will be finalized prior to the First-subject-first-visit for the final analysis of the study. The recommendations of the ICH E9 'Note for Guidance on Statistical Principles for Clinical Trials' including the addendum R1 to ICH E9 will be taken into account.

Unless otherwise stated, continuous data will be summarized by means of descriptive statistics, i.e. number of subjects, mean, standard deviation (SD), median, quartiles and range (minimum and maximum). Categorical variables will be summarized by absolute and relative frequencies (percentages) of subjects by category. Missing values will not be included in the calculation of percentages.

Eligible subjects who withdraw from study participation before IMP administration will be considered as dropouts.

The demographic data from screening failures and dropouts prior to IMP administration are entered into the clinical database and will not be passed through the data cleaning process. Their data are listed separately from data of treated subjects.

Statistical analyses will be conducted using SAS version 9.4 or higher (SAS Institute, 2010).

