14.5 Handling of missing data

Missing data of safety variables will not be replaced. Further details on the handling of missing data will be specified in the SAP.

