## 4.4 Analysis of Endpoints

### 4.4.1 Adverse Events

AEs will be coded by using the Medical dictionary for regulatory activities (MedDRA, MedDRA version available at the day of database closure). If an AE occurs in multiple treatment areas, it is reported separately for each treatment area within the eCRF. Thus, some AEs are counted repeatedly for the analysis.

Analysis will focus on severity and duration of TEAEs. TEAEs are defined as all AEs with onset or worsening after treatment with IMP up to Visit 5 (Final visit). AEs with start on the day of PDT which are unrelated or unlikely related to IMP belonging to AE category 'NEW LESION' and with action taken 'PDT treatment' will be classified as pre-treatment emergent adverse events. If unclear due to incomplete start date/time of AE or IMP application or uncertainty about worsening of AE, AEs will be assumed as TEAEs. AEs developing between signing the ICF and IMP application at Visit 2 will be considered as pre-treatment adverse events (PTAEs). TEAEs as defined above, will be tabulated by system organ class (SOC) and preferred term (PT) (MedDRA). The number of entries, as well as the number and rate of affected subjects will be reported for each treatment area and overall.

TEAEs will also be tabulated by relationship to IMP and/or medical device and by worst severity. TEAEs are considered being related to IMP or medical device, if causal relationship between IMP or medical device and the TEAE is at least possible or relationship assessment is missing. For AEs with changes in severity, the worst severity per AE and subject will be tabulated.

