#### Duration and severity of adverse events

Duration of TEAEs by severity will be presented for related PTs which occurred in at least 2 subjects. For all those TEAEs (related to IMP and/or medical device), the duration of the AEs will be tabulated by severity. For each of these TEAEs, the mean duration of each severity category, based on all subjects who experienced these TEAEs, will be presented in a stacked bar chart. The proportion of days in the different severity categories as a percentage of the total duration will be presented in a frequency table for each TEAE. For the frequency table and the stacked bar charts, the calculations for each severity category will be performed with reference to all subjects who experienced this TEAE, regardless of severity. If a severity category does not occur in a subject, the duration in this category is set to 0. Calculation of duration of severity will only be done for AEs with complete start and stop dates. AEs with incomplete start or stop dates or ongoing AEs will not be considered for this analysis.

If for a TEAE only one severity is recorded during the day, then the duration of the severity of this TEAE will be set to one day. If severity changes during the day, more than one change can be recorded. For the calculation of the duration of each severity category on this day, the day will be

divided by number of changes during the day (so that duration can be e.g. 0.5 day, 0.33 day). Note that on day 1 only one severity is recorded.

Listing will include the start day of TEAEs after PDT. Calculation of TEAE start after PDT is performed in days as follows: start date of TEAE- start date of PDT.

PTAEs will be listed separately and not included in any tables or other listings.

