#### 4.7 Miscellaneous

For qualitative variables the frequencies (absolute and relative) will be calculated. For frequency tables, the number of non-missing values will be presented. Missing values (including user-defined missing values) will not be presented and not included in the calculation of percentages. Percentages will be presented to one decimal place. Details of format of tables, listings and graphs are given in Appendix A, but the real design will be determined by the technical possibilities within SAS and may not look identical to the description. However, all information as mentioned will be included. Only observed outcomes will be displayed in frequency tables. If for a category no data is observed (e.g., females will not be displayed if all subjects are male) this category will not be displayed.

Quantitative parameters will be described by declaring the mean value, standard deviation, minimum, first quartile, median, third quartile, and maximum. In the description of the tables this will be denoted by „basic statistics“. In general, minimum and maximum will be presented to the same level of precision as the raw data; means and medians, standard deviation, and quartiles will be presented to one further decimal place.

The listings are always sorted by treatment area and subject. If a different sorting order should be used for some listings this will be remarked separately. The variables for the special listings are explicitly given in the description of listings. All listings will be presented for the safety analysis set, if not stated differently.

Screening failures and enrolled but not treated subjects (withdrawal before treatment) will be considered in tables and listings describing analysis sets, eligibility and discontinuation and separate demographic listings. Listings including screening failures and enrolled but not treated subjects will be stratified by SAF.

The following title will be used for all generated tables, listings, and graphs:

Protocol: ALA-AK-CT018  
Final Analysis

Page # of #

The numbering NNN of the tables/listings/graphs will be stated in the detailed description (Appendix A).

Following footnote will be used for all generated tables, listings, and graphs:

---

Program: <Name of program> Run date/time: yyyy-mm-ddThh:mm

All tables, listings, and graphs will be generated in A4 paper format.

The statistical evaluation will be performed using SAS version 9.4 or higher.

Signatures

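### Dropping ongoing adverse events from the duration analysis makes the mean total duration too low for a preferred term whose PDT-day reaction never gets a stop date, provided its resolved events average fewer days than that reaction has already lasted

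*SAP*

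**What the plan says.** SAP section 2 and Protocol 14.2 list the duration of TEAEs, broken down by severity, as an endpoint. Protocol 14.4.3 plans the mean total duration, overall and by treatment area.

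SAP 4.4.1 (Duration and severity of adverse events) sets the rules:

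- Scope: "Duration of TEAEs by severity will be presented for related PTs which occurred in at least 2 subjects".
- Exclusion: a duration needs complete start and stop dates, and "AEs with incomplete start or stop dates or ongoing AEs will not be considered for this analysis".
- Severity categories: means and percentages refer to all subjects who had the event, and "If a severity category does not occur in a subject, the duration in this category is set to 0".
- Repeated entries: an event in several treatment areas is entered once per area. "Thus, some AEs are counted repeatedly for the analysis".

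SAP section 4 defines duration as stop date minus start date plus 1. SAP 4.5 rules out imputation, and Protocol 14.5 agrees: "Missing data of safety variables will not be replaced". The supplied text plans no censored or time-to-resolution summary. Protocol 11.3 foresees events that do not resolve, since the outcome codes are "outcome (recovered/resolved, recovering/resolving; recovering with sequelae, not recovered/not resolved, fatal, unknown". It also asks for follow-up beyond the end of the study, which the investigator may end before resolution. The SAP does not say whether stop dates obtained that way enter the analysis.

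**The concern.** Whether an event is left out depends on the quantity being measured. An event is ongoing because it has lasted long, so the rule removes values from the upper tail. Protocol 4.3 says that most reactions begin during or soon after illumination, that most last 1 to 4 days, and that some last 1 to 2 weeks or longer. The tables and stacked bars are meant to show how long reactions last. As written, a reaction that never closes adds nothing to them. Because terms are reported from two subjects upward, one open event can dominate a small term.

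**Working it through.** The documents state no expected duration, standard deviation or rate of ongoing events, so there is no planned figure to reproduce. The check is a lower bound under stated assumptions.

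**Minimum length of an excluded event.** Visit 5 falls 28 ± 7 days after PDT. With onset on the PDT day (day 0) and the SAP's inclusive formula, an event still open at Visit 5 has lasted at least 21 + 1 = 22, 28 + 1 = 29 or 35 + 1 = 36 days.

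**Direction.** Leaving out a value larger than the mean of the rest lowers the mean. The reported mean is therefore too low whenever the resolved events average fewer days than the excluded event has already lasted.

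**Size with one ongoing event among n affected subjects.** Let m be the resolved mean and d the day of last contact. The plan reports m. The mean over all events is at least B = [(n − 1)m + d + 1]/n, and the shortfall is at least 1 − m/B. Assumed: m = 4, d = 28.

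| n | B (days) | Shortfall at least |
|---|---|---|
| 2 | (4 + 29)/2 = 16.5 | 76% |
| 10 | (36 + 29)/10 = 6.5 | 38% |
| 20 | (76 + 29)/20 = 5.25 | 24% |
| 50 | (196 + 29)/50 = 4.50 | 11% |
| 100 | (396 + 29)/100 = 4.25 | 6% |

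Range at n = 20:

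- Last contact at day 21 gives B = 4.90 (18%); day 35 gives B = 5.60 (29%).
- At day 28, m = 2 gives B = 3.35 (40%); m = 8 gives B = 9.05 (12%).

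**Light tail.** Assume exponential durations with median 4 days, so the mean is μ = 4/ln 2 = 5.77. With a cut at τ and q = exp(−τ/μ), the resolved mean is μ − τq/(1 − q). For τ = 21, 28 and 35 this is 5.20, 5.55 and 5.69 days, or 9.8%, 3.8% and 1.4% low.

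**Median.** In the same exponential case the resolved median is −μ·ln[1 − (1 − q)/2] = 3.85, 3.96 and 3.99 against 4.00, at most 3.7% low. With two subjects (one resolved at 4 days, one open at day 28) the planned median is 4 and the all-event median is at least 16.5, the same shift as the mean.

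**Stop dates after Visit 5.** Assume 5% of events are ongoing at day 28 and all of them last to day 42 (43 days). The full mean is 0.95 × 4 + 0.05 × 43 = 5.95. If a share c of them is closed and used, the plan gives (3.8 + 0.05c × 43)/(0.95 + 0.05c). For c = 0, 0.5 and 1 this is 4.00, 5.00 and 5.95: 33%, 16% and 0% short.

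**Single severity categories.** Assume a resolved event has 1 severe, 1 moderate and 2 mild days, and 5% of events are ongoing to day 28 with s severe days each. Total days are 0.95 × 4 + 0.05 × 29 = 5.25, and the severe mean is 0.95 + 0.05s. The plan reports a severe mean of 1.00 and a severe share of 25.0%.

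| s | Severe mean, all events | Severe share | Plan is |
|---|---|---|---|
| 0 | 0.95 | 18.1% | too high on both |
| 3 | 1.10 | 21.0% | too low on the mean, too high on the share |
| 10 | 1.45 | 27.6% | too low on both |

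So the direction is settled for the total duration but not for single categories.

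**The case against.** The exclusion is prespecified, openly stated and consistent with the no-replacement rule. Nothing in the documents shows that any reaction will be open at day 21 to 35; the bulk last 1 to 4 days, and the light-tail case loses under 10%. The 76% figure needs a two-subject term. Ongoing events should also be traceable. Protocol 14.4 lists all variables for treated subjects, and Protocol 14.4.3 lists subjects with AEs. Protocol 14.1 summarises continuous data by "number of subjects, mean, standard deviation (SD), median, quartiles and range (minimum and maximum", and SAP 4.7 adds that "For frequency tables, the number of non-missing values will be presented". Table details are in Appendix A of the SAP, which was not available. With about 100 subjects, counts and a sentence on late stop dates would go a long way.

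Most of this stands and limits the weight of the point. It does not restore the open events to the duration summaries. Counts of analysed or affected subjects do not show how many events were left out, or why.

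A reader might infer more than the documents support:

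- **That every term with an event open at Visit 5 is understated.** If the stop date is later obtained and used, there is no bias. The direction can also reverse: resolved durations of 33 and 34 days with an excluded event truly lasting 25 (Visit 5 on day 21) give 33.5 reported against 30.7. That needs a resolved mean above about 22 days, which does not fit Protocol 4.3.
- **That the direction is known for every excluded event.** It is uncertain for late-onset events, partial dates and early withdrawals.
- **That excluded events are scored as 0 days.** The zero rule covers a severity category that does not occur, not an excluded event. Referring the means to all subjects with the event leaves room for doubt, so a clarifying clause is enough.

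**Conclusion.** The point holds in a bounded form and should be fixed. For a preferred term with a PDT-day reaction that has no stop date at database lock, the planned mean total duration is too low as long as the resolved events average fewer days than that reaction has already lasted. Protocol 4.3 makes that condition the expected one.

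The size cannot be known from the documents. The illustrative shortfalls rest on an assumed 4-day resolved mean, PDT-day onset and a single event open at day 28. The median is little affected in larger terms but can move as much as the mean in very small ones. No hypothesis or decision rule depends on these figures; the consequence is a description of tolerability that leaves out the reactions that did not close.

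**What to change.** Keep the completed-event tables and stacked bars, and add to SAP 4.4.1:

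1. For each related preferred term, the number of events analysed, the number (%) ongoing at last contact by severity, and the number excluded for partial dates.
2. A Kaplan-Meier summary of time to resolution (median, quartiles) for terms with at least one ongoing event and enough subjects for a meaningful curve. Censor ongoing events at last contact, or at the last visit date if no later contact is recorded. For smaller terms, list the ongoing events individually. If a restricted mean is given, restrict it to 22 days, or to the longest time observed for that term if shorter. Note that 22 days of observation is assured only for PDT-day onset in completers.
3. A rule that merges only entries for the same episode repeated across treatment areas. Separate episodes stay separate, so that symptom-free gaps are not counted.
4. A sentence that excluded events leave the denominator and are not scored as 0 days.
5. A sentence on whether stop dates obtained after Visit 5 are used.

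Censoring fills in no stop date, so it respects the no-replacement rule. A mean that runs open events to last contact should be only a supplement, labelled as a lower bound.

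The cost is one extra table per preferred term and some wording. Dates, severity changes and outcome are already collected under Protocol 11.3; a contact date after Visit 5 may not be, hence the fallback in item 2. Kaplan-Meier assumes that early withdrawal is unrelated to the course of the reaction, and a restricted mean says nothing beyond its limit.

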#### Adverse events of special interest

A medical review of all adverse events will be done during the data review meeting to identify adverse events of special interest (AESIs) as specified in Note to File no. 4 to the protocol version 3.0.

AESIs will be tabulated by SOC and PT stratified by SAE (yes/no).

#### Application site reactions

A frequency table showing number and proportion of subjects with application site skin reactions and application site discomfort will be displayed. Per subject the maximum intensity will be displayed if more than one application site skin reactions and application site discomfort occurred.

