BF-200 ALA is a gel formulation of 10 % 5-aminolevulinic acid hydrochloride, corresponding to 7.8 % 5-aminolevulinic acid (ALA). It is approved as Ameluz® by the Food and Drug Administration (FDA) in combination with photodynamic therapy using BF-RhodoLED® lamp and indicated for the lesion-directed and field-directed treatment of actinic keratoses (AK) of mild to moderate severity on the face and scalp. The IMP will be packed in tubes, containing 2 g each. Three tubes will be applied per subject.

Investigational medical device (IMD)

The study treatment requires illumination of the treatment field with ~37 J/cm² of red-light at ~635 nm. Approved for PDT in combination with Ameluz® is the BF-RhodoLED® lamp. In this study, the BF-RhodoLED® XL will be used which allows the illumination of a larger area than the BF-RhodoLED®.

Study Duration and Dates

Each subject will be in the study for approx. 6 weeks.

Within 14 days after the screening visit (Visit 1) and following confirmation of eligibility, subjects will be treated with PDT (Visit 2). At Visit 3 (7 days post PDT) and Visit 4 (14 days post PDT) assessment of transient side effects will be performed. At Visit 5, 28 days post PDT, the final evaluation of safety and tolerability will be performed.

In-/exclusion criteria

Inclusion criteria

1. Willingness and ability of subjects to provide informed consent and sign the Health Insurance Portability and Accountability Act (HIPAA) form. A study-specific informed consent and HIPAA form must be obtained in writing prior to starting any study procedures.
2. Subjects with mild to severe clinically confirmed AK lesions (according to Olsen (Olsen et al., 1991)) on the face and/or scalp. In case of severe AK lesions, a biopsy must be taken for confirmation of diagnosis. At least 8 mild to moderate AK lesions with a diameter of ≥ 4 mm must be present in the treatment field. The treatment field (continuous or in several patches) totaling about 60 cm² must be located within one effective illumination area. The AK lesions should be clearly distinguishable, without restrictions on the distance between lesions. Lesions should have a minimal distance of 1 cm between the lesion margin and the border of the treatment field.
3. All sexes, ≥ 18 years of age.
4. Willingness and ability to comply with study procedures, particularly willingness to receive a PDT session and to undergo 2 mm punch biopsy/biopsies in case of severe AK lesion(s) at the screening visit.

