4.3 Risk/benefit analysis

This safety study will include diseased subjects presenting with at least 8 mild to moderate AK lesions (≥ 4 mm) within the treatment field of about 60 cm² in total. In addition, severe AK lesions may be present in the treatment field. Subjects will receive BF-200 ALA treatment - already marketed for the treatment of AK in the US, EU, and Switzerland under the brand name Ameluz[®] - with conventional red-light illumination.

Clinical efficacy and safety of BF-200 ALA in combination with conventional red-light illumination for the treatment of mild to moderate AK on the face and scalp were previously examined in one dose-finding study, and three confirmatory studies encompassing a total of 885 randomized subjects comprising 462 subjects (2674 lesions) exposed to BF-200 ALA (7.8% ALA) (23–25) treated on the face and scalp. All subjects received up to 1 tube (2 g) of BF-200 ALA. In these pivotal clinical trials, complete response of subjects 12 weeks after the last PDT with BF-200 ALA was shown to be up to 90.9 % and total lesion response was up to 94.3 % (23–26).

In previous clinical trials with BF-200 ALA, local application site reactions were observed in 84-100 % of the subjects. These reactions are expected, given the therapeutic principle of PDT, which is based on phototoxic effects. The most common signs and symptoms were application site erythema, pain/burning, irritation, and edema. Most adverse reactions occurred during illumination or shortly afterwards. Symptoms were usually of mild or moderate intensity (investigator's assessment on a 4-point scale). Subjects treated with a higher dose (6 g / 3 tubes BF-200 ALA) within an enlarged treatment field of 60 cm² experienced more severe application site reactions (mainly pain, erythema) when treated on the face and scalp which was not reported for subjects treated in the periphery. Given that PDT pain was already described to be related to the size of treatment field (27), a higher pain intensity during treatment of an expanded treatment field on the face and/or scalp was to be expected. Nonetheless, application site pain during PDT is transient and well manageable. In most cases the symptoms lasted for 1 to 4 days, however, in some cases, they persisted for 1

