14.4.3 Evaluation of the Safety Endpoints

Safety analyses

All safety endpoints will be analyzed descriptively and in an exploratory way. These safety analyses will be performed for the safety set. Selected safety analyses will be conducted overall and stratified by age groups, sex, skin type, and treatment area.

AEs will be coded according to the latest Medical Dictionary for Regulatory Activities (MedDRA) version available at the day of database closure. The analysis will focus on the TEAEs. TEAEs will be summarized and tabulated according to primary system organ class and preferred term. TEAEs leading to death and TEAEs resulting in discontinuation of study will be tabulated using frequency tables.

The mean total duration of TEAEs including the breakdown of severity category (mild, moderate, severe) will be presented overall and by treatment area.

A listing of subjects with AEs will be provided for all subjects in the SAF.

The frequency of application site skin reactions and of application site discomfort will be presented overall, and per treatment area. The mean pain score (NRS-11) and the respective confidence intervals (CIs), and the range will be presented overall and by treatment area.

All laboratory values will be classified as normal or abnormal according to the laboratory's normal ranges and indicated as clinically significant or non-clinically significant by the investigator. Frequency tables for clinically significant findings will be provided. Laboratory values that are out of range and considered clinically significant will be additionally documented in the medical history (Visit 1) or as AEs (28 days after the PDT, Visit 5) and listed as such.

The analyses of variables for vital signs will focus on

- A) the evaluation of the change from baseline (Visit 2, first measurement after the subject arrived at the site) to values on subsequent clinical visits and
- B) The evaluation of the change on Visit 2 from baseline (first measurement after the subject arrived at the site) to values obtained prior and after illumination (until 60 min post illumination).

Descriptive analysis (number of subjects, mean, median and SD, minimum, maximum) of the time course and of changes from baseline to post baseline time points will be presented.

Physical examinations will include the following body systems: head, neck, skin, lymph nodes, thorax including heart and lung, abdomen, and musculoskeletal, peripheral vascular and nervous system.

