## 2 Endpoints

The endpoints of the study are:

- Frequency and severity of adverse events (AEs), serious AEs (SAEs), and treatment-emergent adverse events (TEAEs). TEAEs are defined as all AEs with onset or worsening after treatment with IMP up to Visit 5
- Duration of TEAEs including the breakdown of severity category (mild, moderate, severe)
- Assessment of new lesions (AK, non-melanoma skin cancer (NMSC) such as basal cell carcinoma (BCC), squamous cell carcinoma (SCC) or Bowens disease and melanoma) if they occur inside the treatment field
- Assessment of new lesions (AK, NMSC such as BCC, SCC or Bowens disease and melanoma) if they occur around the treatment field at a distance of < 10 cm
- Application site skin reactions during and post PDT, assessed by the investigator
- Application site discomfort during and post PDT, reported by the subjects
- Application site pain during illumination, as assessed by the subjects using an 11-point numeric rating scale
- Changes in vital signs
- Safety laboratory data
- Physical examination data
- Neurological assessments

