### **4.4.3 Overall Tolerability**

#### Application site skin reactions during and post PDT

Details regarding application site skin reactions (erosion, erythema, exfoliation, oedema, fissure, induration, vesicles, ulceration, flaking, scabbing, discharge, other) will be listed.

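### The one table dedicated to application site reactions has no time split, and the duration outputs drop reactions still ongoing, so no stated summary gives the proportion affected at Visits 3, 4 or 5

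*SAP*

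**What the plan says.** Two of the endpoints in SAP section 2 cover the period after treatment as well as the treatment itself. One reads "Application site skin reactions during and post PDT, assessed by the investigator"; the other is the matching endpoint for discomfort reported by subjects. The protocol outline says that at Visits 3 and 4 "assessment of transient side effects will be performed". Protocol 10.1.2 to 10.1.5 and 10.2.7 have reactions assessed within 10 min and at 60 min after illumination, and again at Visits 3, 4 and 5.

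The planned reporting is as follows.

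- **Dedicated table (SAP 4.4.1, Application site reactions).** "A frequency table showing number and proportion of subjects with application site skin reactions and application site discomfort will be displayed". The rule within a subject is: "Per subject the maximum intensity will be displayed if more than one application site skin reactions and application site discomfort occurred". No visit or period is named.
- **Protocol 14.4.3.** "The frequency of application site skin reactions and of application site discomfort will be presented overall, and per treatment area". There is no visit split here either.
- **SAP 4.4.3, Overall Tolerability.** Listings only: "Details regarding application site skin reactions (erosion, erythema, exfoliation, oedema, fissure, induration, vesicles, ulceration, flaking, scabbing, discharge, other) will be listed". Discomfort is handled the same way.
- **TEAE outputs (SAP 4.4.1).** Protocol 10.2.7 and 11.3 make these reactions AE records with their own category, start and stop times and dated severity changes. They therefore enter the tables by SOC and preferred term, by relationship and worst severity, and by subgroup. Related preferred terms seen in at least 2 subjects also get a duration-by-severity table, a percentage-of-days table and stacked bar charts. Ongoing events and events with incomplete start or stop dates are left out of that duration analysis. The start day after PDT is only listed.

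**The concern.** Protocol 4.3 reports that "local application site reactions were observed in 84-100 % of the subjects" in earlier trials, mostly during illumination or shortly afterwards. A table of any reaction, graded at its maximum, will therefore mostly describe the treatment day. Persistence is the less certain quantity. The same section says that symptoms usually lasted 1 to 4 days but sometimes 1 to 2 weeks or longer, and that reactions were more severe with 3 tubes on 60 cm² of the face and scalp, which is the use studied here.

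A reader of the final report will want to know how many subjects still had a reaction one, two and four weeks after treatment, and how severe it was. The visits collect what is needed to answer that. Vital signs are summarised by visit and time point (SAP 4.4.4), but these two endpoints are not.

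**Working it through.** The plan has no figure to reproduce: no sample size was calculated and no prevalence by visit is stated. The check asks which of the planned outputs would change if persistence changed.

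**Inputs from the documents.** About 100 subjects (SAP 1.3); 84-100 % with a local reaction, mostly on the treatment day (Protocol 4.3); duration = stop date − start date + 1 (SAP 4); ongoing events excluded from the duration analysis (SAP 4.4.1).

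**Assumptions.** 92 of 100 subjects react, the midpoint (84 + 100)/2. Each has one reaction, with the same preferred term, which starts and peaks on the PDT day. Resolved reactions last 3 or 16 days. Ongoing reactions have no stop date at database closure.

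**Step 1: how close to the ceiling.** Exact (Clopper-Pearson) 95 % intervals at N = 100 are 75.3-90.6 % for 84/100, 84.8-96.5 % for 92/100 and 96.4-100 % for 100/100.

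**Step 2: four persistence patterns.** A reaction of d days that starts on the PDT day is last present d − 1 days after PDT.

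| Pattern | Dedicated table | Present at Day 7/14/28 after PDT | Mean duration, planned rule | n in mean |
|---|---|---|---|---|
| A: all 92 last 3 days | 92 % | 0/0/0 | 3.0 | 92 |
| B: 62 last 3 days, 30 last 16 days | 92 % | 30/30/0 | (62×3 + 30×16)/92 = 666/92 = 7.24 | 92 |
| C: 82 last 3 days, 10 ongoing | 92 % | 10/10/10 | (82×3)/82 = 3.0 | 82 |
| D: 62 last 3 days, 30 ongoing | 92 % | 30/30/30 | (62×3)/62 = 3.0 | 62 |

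The dedicated table is identical in all four, because the peak is on the PDT day in each. The duration table separates A from B. Its means do not separate A from C or D; only the number analysed changes.

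**Step 3: a milder contrast, to be fair to the duration table.** Assume 95 subjects react and either 10/2/0 or 60/30/10 subjects are still affected at Days 7/14/28. Assign 3, 10 or 21 days to reactions that clear before Day 7, between Days 7 and 14, or between Days 14 and 28.

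- First case: (85×3 + 8×10 + 2×21)/95 = 377/95 = 4.0 days.
- Second case, with the 10 ongoing dropped: (35×3 + 30×10 + 20×21)/85 = 825/85 = 9.7 days.

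Here the planned duration output does show the difference.

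**Step 4: what a by-visit table would deliver.** With 100 subjects assessed, exact 95 % intervals would be 0-3.6 % for 0/100, 1.6-11.3 % for 5/100, 4.9-17.6 % for 10/100 and 21.2-40.0 % for 30/100. These counts are illustrative.

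**The case against.** The strongest reply is that persistence is already covered. Duration of TEAEs by severity is itself a named endpoint, its analysis includes these reactions, and days of duration are finer than visits with windows of ±2 or ±7 days. The SAP also delivers what Protocol 14.4.3 promises, which contains no visit split, and the study is descriptive.

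Much of this stands. A reader might infer that the dedicated table is the only one in which these reactions appear, or that nothing tabulated addresses the time after PDT. SAP 4.4.1 does not support either reading: the TEAE tables contain the reactions, and the duration outputs separate short from long resolved ones (Steps 2 and 3). A reader might also infer that the dedicated table is uninformative. It is not, because the split by maximum intensity can vary even when nearly everyone reacts. That its maximum is taken over the whole study is itself an inference, since no period is stated.

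The reply does not reach three things.

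- The tables by SOC and preferred term, relationship, worst severity and subgroup have no time dimension.
- The duration outputs work per preferred term. They cannot give the number of subjects with any reaction on a given day.
- They leave out events without a stop date. Comparing the number analysed with the TEAE count would hint at this, but it would mix ongoing events with incompletely dated ones.

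Protocol 11.3 lets events be followed beyond the end of the study, so some late stop dates may be obtained. The exclusion then affects only those that are not.

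**Conclusion.** The point holds as a reporting gap in two named endpoints. The dedicated table will be near its ceiling for any reaction and driven by the PDT day. The only planned summary of persistence is indirect and can lose the longest-lasting reactions. In the illustration, 0 or 30 of 92 affected subjects still reacting at Visit 5 give the same dedicated table and the same 3.0-day mean.

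The 84-100 % range and the early timing come from the protocol. The 92 affected, the durations and the ongoing counts are assumptions, and so is a peak on the PDT day for every subject. The conclusion is limited to the protocol and SAP text. SAP section 4 refers the detailed table descriptions to Appendix A, which was not available, so a by-visit table there cannot be ruled out. If one exists, SAP 4.4.3 should say so, because it now promises only listings.

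**What to change.** Add one table to SAP 4.4.1 or 4.4.3. It should give the number and percentage of subjects with application site skin reactions and, separately, with discomfort, by worst severity present on the PDT day and at Visits 3, 4 and 5, overall and by treatment area.

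- Use the subjects assessed at that visit as the denominator.
- Derive presence and grade from the AE start, stop and severity-change dates that Protocol 11.3 already requires.
- Count ongoing events as present, and show the number still ongoing at Visit 5.
- State in advance how events with incomplete dates are classified.
- Keep the PDT day as a single column, since Protocol 11.3 asks only for the maximum severity on an event's first day.

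The cost is one derived table, somewhat coarse because of the visit windows. No new data are needed, and the planned duration outputs can stay as they are.
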